Participants will be provided with a seven-day supply of progesterone or placebo. Randomization to treatment will be done by the MUSC Investigational Drug Service (IDS). Dosing will begin in the evening on study day 1. On study days 2-7 participants will take medication at home in the morning and evening, and on day 8 the final dose will be taken at in the morning prior to completion of the laboratory stress task (described below). Progesterone and matching placebo capsules will be prepared and dispensed by the MUSC IDS. Previous studies (Fox et al., 2013; Sofuoglu et al., 2001; 2011) have used twice daily administration of 200mg progesterone during the early follicular phase to achieve stable levels of progesterone comparable to normal luteal phase levels (2-20 ng/ml). Safety and tolerability of micronized progesterone have been established in numerous studies with nicotine (Sofuoglu et al., 2001; 2011) and cocaine (Evans & Foltin, 2006; Fox et al., 2013; Reed et al., 2011 Sofuoglu et al., 2002; 2004) dependent individuals.

c. Cannabis Abstinence Verification. Cannabis abstinence will be assessed using self-report, saliva drug testing, and cannabinoid levels. Self-report will be collected at study visits using the TLFB as well as collected daily through mobile surveys or “morning reports” completed via mobile electronic device. Participants will be trained to self-administer saliva drug screening (Oratect FDA approved saliva test.). This test is able to detect THC in saliva for up to 14 hours. Participants will be instructed to complete two saliva drug tests daily using the RedCap video upload procedure described below under *Medication Adherence/Drug Test Monitoring*. A test will be completed in the office on Day 1 so patients can practice the procedure. Cannabinoid levels will also be assessed using urine toxicology collected on Study Days 8 and 22. Creatinine-corrected cannabinoid levels will be compared from Day 1 to Day 8 to confirm abstinence during the study period. Our group has recently published on the need for utilization of multiple methods to determine cannabis abstinence (Baker et al., in press). Contingency management (monetary compensation) procedures will be incorporated to promote abstinence (described below).

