d. Medication Adherence/Drug Test Monitoring. Participants will record themselves taking their morning and evening medication doses as well as completing the twice daily saliva drug test swab procedure. Photos of the completed saliva test will be uploaded. A survey link will be sent to the participant’s (or study provided) cell phone via CREMA app alert twice daily. Video capture will occur as part of a RedCap survey. As discussed in the Preliminary Data section, we have previously utilized this technology successfully for both medication adherence monitoring and to remotely assess substance use. To encourage compliance with study procedures, participants will receive \$10 for completion of each medication adherence video. Participants will receive an additional \$30 for each saliva drug screen that is negative for all drugs of abuse. A similar compensation schedule was effective in our pilot progesterone study. Study staff will call participants twice during this week to see if they are having any difficulties with the procedures or side effects from the medication. Study staff will also text abstinence reminders to patients whose saliva tests positive for drugs of abuse.

e. CREMA Assessment. Cue Reactivity Ecological Momentary Assessment (CREMA; Warthen & Tiffany, 2009; Wray, Godleski, & Tiffany, 2011; Wray et al., 2015) is a cue reactivity assessment in which photographic stimuli are presented multiple times per day on a mobile electronic device (i.e iPhone). In cases where participants do not have a smart phone or do not wish to use their own device for the purposes of the study, a phone will be provided. Participants will be instructed to keep their phone with them at all times. Phones will be password protected to prevent access to the study assessments and surveys by anyone other than the participant. Auditory alarms will alert participants to complete three, randomly scheduled CREMA sessions per day (session duration = 3-4 minutes). Alarms will be distributed over a 12-hour period, divided into three, 4-hour blocks with a minimum time of 30 minutes between alarms/CREMA sessions. In order to accommodate varying participant wake-sleep schedules, participants will be able to choose the 12-hour period during which they will be prompted and this may vary from weekdays to weekends. There will be two types of picture cues that differ based on content:

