C.2.c.4. Laboratory Stress Induction Session (Day 8). Following the one-week period of progesterone or placebo administration, participants will return to the study clinic to complete a laboratory stress task (Trier Social Stress Test, TSST). Data from this task will be used to complement the “real world” stress reactivity data collected via CREMA. If participants become unable to attend the session on Day 8, they may be re-scheduled for the following day. However, participants will not be re-scheduled after Day 9.

a. Session Preparation. Participants will be instructed to arrive at 11:00am on the day of the TSST, and to avoid caffeinated beverages on the test day since caffeine can inflate reactivity to the stressor. If the individual is nicotine-dependent, (s)he will be provided with a nicotine patch throughout their study visit. Upon arrival, the participant will be breathalyzed and will provide urine and saliva samples, which will be tested for the presence of marijuana, cocaine, opiates, barbiturates, benzodiazepines, and stimulants. The urine sample will also be quantitatively analyzed for cannabinoids and creatinine to confirm past week cannabis abstinence. At 10:30am, saliva (progesterone) will be collected, and a blood pressure cuff will be placed on the participant’s arm. Two baseline assessments of subjective, hormonal (cortisol; see Assessments below for details), and physiologic measures (blood pressure and heart rate) will be collected, one at 11:40am and the second at 11:55am.

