b. TSST. The TSST is a standardized psychological stress challenge which has been used extensively in research studies. A meta-analysis supports its utility for provoking a HPA axis stress response in a laboratory setting (Dickerson & Kemeny, 2004). We have used it in our previous work to induce a robust and reliable physiological stress response in cocaine, alcohol, and cannabis-dependent individuals (McRae et al., 2006; [name] et al., 2011; Waldrop et al., 2010). At 12:00pm, the participant will be told that (s)he will give a speech and perform an arithmetic task. The topic of the speech will be why (s)he should be hired for a particular job (the individual’s “dream job”). The participant will deliver the speech as though speaking to a group of potential employers. The experimenter then tells the participant that (s)he has 5 minutes to prepare the speech and starts the countdown clock (placed in view of the individual). The experimenter leaves the room to allow the participant to prepare. Five minutes later, three individuals unfamiliar to the participant (the audience) enter the room and are seated; the individual will be instructed by one audience member to stand and begin his/her prepared speech (without notes). The speech will be delivered for 5 minutes. If the individual pauses, (s)he will be instructed to continue. At the end of the speech task, the individual will be instructed to serially subtract 13 from 1,022 as quickly and accurately as possible. The mental math recitation will continue for 5 minutes, at the end of which time, the spokesperson will instruct the individual to stop and be seated, and the audience leaves the room. At this point, a saliva sample will be collected (for cortisol) and physiological (blood pressure and heart rate) and subjective measures (Within Session Rating Scale, Marijuana Craving Questionnaire, STAI) obtained. Measurements will also be obtained at 5-, 30-, and 60-minutes post-task.

Modifications may be made to TSST procedures if necessary for patient and staff safety, ie fewer confederates, remote procedures.

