queried three times daily regarding stress and craving levels (as assessed by the Within Session Rating Scale), as well as cannabis use in order to determine precipitants of, and sex differences in, return to use. As detailed above, two of these sessions will also include picture presentations (one neutral picture session and one stress-related picture session) to continue to assess stress reactivity during this period. Daily saliva samples will also be collected by participants as above. This monitoring will continue for two weeks following the laboratory stress session. At the end of the two weeks, on Day 22, participants will return to the clinic. At this visit, participants will return collected salivary hormone samples, provide a urine drug screen to validate self-reports of drug use, turn in any clinic-provided phones, complete a questionnaire regarding their experience with the CREMA and REDCap surveys, and be provided referrals to treatment if interested.

Participant Compensation: Participants will be compensated \$40 for completing the screening visit (\$20 for physical, \$20 for interview) and \$20 for Day 1. Participants will receive \$5 for each completed CREMA session, for a total possible compensation of \$300. Participants will receive a \$5 bonus for each day they complete all 3 sessions for a possible total of \$100. During the cannabis abstinence and progesterone administration period, participants can earn a total of \$120 for completing saliva tests \$360 for negative salivary drug tests and \$140 for completing medication adherence video uploads. Participants will receive \$190 for daily collection of salivary samples for ovarian hormone measurements. Participants will also be compensated \$100 for Study Visit 8 (\$50 if they re-schedule for Day 9) and \$100 for Study Visit 22, for a total potential compensation of \$1470. If they borrowed an iPhone and do not return it they will be paid \$50 for Visit 22. ClinCards may be mailed to participants or obtained at their first clinic visit. Participants will complete a w-9 which may be done in person or via Doxy.me.

Confidentiality: Confidentiality of all research data will be maintained by keeping all data in a locked file, limiting access to the computer database to only study personnel, and by using patient code numbers as opposed to names on all paperwork.

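### A stress session moved to Day 9 has no stated dosing rule, and the 14 doses supplied cannot carry twice-daily dosing up to it without a break

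*Combined protocol and SAP*

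**What the plan says.** C.2.c.3 item b (micronized progesterone): "Participants will be provided with a seven-day supply of progesterone or placebo". Dosing starts on the evening of Day 1 and is twice daily on Days 2 to 7. Then "on day 8 the final dose will be taken at in the morning prior to completion of the laboratory stress task". The same paragraph justifies the regimen by earlier studies that used "twice daily administration of 200mg progesterone during the early follicular phase to achieve stable levels of progesterone" in the normal luteal range.

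C.2.c.4 (laboratory session): "If participants become unable to attend the session on Day 8, they may be re-scheduled for the following day", with Day 9 as the latest day. Item b of that section fixes the clock: "At 12:00pm, the participant will be told that (s)he will give a speech and perform an arithmetic task".

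C.2.c.3 item d pays USD 10 "for completion of each medication adherence video". The compensation paragraph in C.2.c.5 allows a total of USD 140 "for completing medication adherence video uploads". It lowers the visit payment from USD 100 to USD 50 "if they re-schedule for Day 9". That is the only other place where Day 9 appears, and it gives no dosing instruction.

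C.2.d.1 makes randomized treatment the main predictor of TSST response in Aim 2 and does not mention sessions held on Day 9.

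**The concern.** The plan wants the TSST done on treatment: the last dose is placed on the morning of the test, after a week of regular twice-daily dosing meant to hold progesterone stable. The Day 9 option breaks that link, because neither the dosing paragraph nor the session paragraph says what a participant should take once the session moves.

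The TSST is a single session that carries all of Aim 2. Participants in the progesterone arm who are tested on Day 9 may have lower or less stable exposure than those tested on Day 8. If so, the estimated treatment effect, and the treatment-by-sex interaction with it, would shrink towards zero. Without a rule, staff may also handle moved sessions in different ways, and the analyst could not tell which course was followed.

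**Working it through.** **1. Reproduce the plan's dose count.** Day 1 evening gives 1 dose, Days 2-7 give 6 × 2 = 12, and Day 8 morning gives 1. The total is 1 + 12 + 1 = 14. A seven-day supply taken twice daily is 7 × 2 = 14. The payments agree: USD 140 / USD 10 = 14 videos. With full adherence and exact dispensing, 14 − 14 = 0 doses remain after Day 8 morning.

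**2. Doses needed for a Day 9 session.** Day 1 evening, Days 2-8 twice daily and Day 9 morning make 1 + 7 × 2 + 1 = 16. The shortfall is 16 − 14 = 2 dose times, whichever two are skipped.

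**3. What happens under each reading.** No clock time is given for doses. I assume 6-10am for morning doses and, where needed, 6-10pm for evening doses. The task starts at 12:00pm.

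| Course followed | Dose times skipped | Last dose to task |
|---|---|---|
| Session on Day 8, as planned | none | 2-6 h |
| Day 9, last dose taken on Day 8 morning (literal reading) | Day 8 evening, Day 9 morning | 26-30 h |
| Day 9, last dose held for Day 9 morning | Day 8 morning, Day 8 evening | 2-6 h |

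The 24-hour difference between the first two rows does not depend on the assumed clock time. In the third row the break falls earlier: from a Day 7 evening dose at 6-10pm to a Day 9 dose at 8am (assumed) is 34-38 h.

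**4. Possible effect on Aim 2.** Let q be the share of sessions moved, equal across arms and sexes, and r the fraction of the progesterone effect that remains on Day 9. The average effect is multiplied by 1 − q(1 − r). Neither q nor r is in the documents, and r may differ between the two Day 9 courses. For scale, 160 randomized less the plan's 10% attrition leaves 160 × 0.9 = 144 sessions, so q = 2%, 5% and 10% means about 3, 7 and 14 moved sessions.

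| q (assumed) | r = 0 | r = 0.5 | r = 1 |
|---|---|---|---|
| 2% | 0.98 | 0.99 | 1 |
| 5% | 0.95 | 0.975 | 1 |
| 10% | 0.90 | 0.95 | 1 |

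**5. Is the Day 9 option worth keeping?** Keeping moved sessions scales the expected test statistic by 1 − q(1 − r). Losing them scales it by √(1 − q). The two are equal at r = 1 − (1 − √(1 − q))/q, which is 0.497, 0.494 and 0.487 for q = 2%, 5% and 10%. A moved session is better than a lost one once about half the effect remains.

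**The case against.** **The literal reading is not the only one.** The dosing sentence names Day 8 but also ties the final dose to the stress task, so a site could reasonably hold that dose for Day 9 morning. This stands. A reader might infer that every moved participant is tested 26-30 hours after the last dose. The documents do not support that: the hours rest on an assumed dose time, and the 24-hour shift holds only on the literal reading. What survives both readings is the shortfall of two doses.

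**There may be capsules left.** A missed dose earlier in the week leaves one over. True, but that dose time was itself skipped, so unbroken dosing is still not achieved.

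**A rule may exist elsewhere.** The Biostatistics Resource Core and the pharmacy and site procedures are not among the documents, so this cannot be excluded.

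**The effect is probably slight.** Day 9 is the limit, the visit payment is halved and reminders are used, all of which favour few moves. C.2.c.4 describes TSST data as complementing the ambulatory data, and the interaction sample size in C.2.d.3 refers to the 7-day ambulatory period. This stands. A reader might want to turn the factors above into a loss of power for Aim 2, but the plan gives no TSST effect size to support one.

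**More doses do not make Day 9 the same as Day 8.** This also stands. Payment for negative saliva tests is USD 360 at USD 30 each, so 360 / 30 = 12 tests, or six days at two a day. Nothing visible extends paid testing to the extra day, so moved participants may also differ in abstinence. An added dosing day also runs slightly later in the cycle for women, whereas C.2.c.3 places treatment in the early follicular phase to limit interaction with endogenous hormones.

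**Conclusion.** The point holds as a gap in the protocol text. It allows a Day 9 test, supplies exactly enough drug for a Day 8 test, and does not say what to do in between. On either reading, 14 doses cannot give uninterrupted twice-daily dosing up to a Day 9 session. That conclusion rests on the documents' own counts. The interval in hours needs the assumed 6-10am dose and the literal reading.

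The consequence is a possible small dilution of the Aim 2 effect, of unknown size. Over the assumed range the factor runs from 0.90 (10% moved, no effect retained) to 1 (full effect retained). It is not a validity problem: the comparison by randomized arm remains sound, and Aim 1 uses data from the week on drug. This is a low-priority, cheap improvement.

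**What to change.** Keep the Day 9 option and make these changes:

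- State in C.2.c.3 item b and in C.2.c.4 that twice-daily dosing continues through the morning of the actual TSST. If such a rule already exists in pharmacy or site procedures, bring it into the protocol.
- Dispense two spare doses on Day 1, in both arms, for use only if the session moves. Someone who cannot attend on Day 8 cannot collect them then.
- Record the session day and the time of the last dose.
- Extend the adherence-video survey and payment to the extra day, and preferably the saliva abstinence tests as well. Update the compensation totals in C.2.c.5.
- Keep the Aim 2 analysis by randomized arm. The saliva progesterone already planned for the session can be summarized by session day as a descriptive exposure check.
- For moved participants, start the Aim 3 endogenous-progesterone window after the actual last dose. This fits that aim's definition of the window as following the end of active medication.

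Costs: up to 2 × 160 = 320 spare doses to dispense and account for. Each moved participant has one more day on drug, slightly later in the cycle for women, and 2 × USD 10 = USD 20 more in videos. If the final visit stays on Day 22, the Aim 3 window for these participants is 22 − 9 = 13 days instead of 22 − 8 = 14. Extending the saliva tests would add their own payments.

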At the start of each CREMA session, participants will be asked to stop using cannabis (if they are at the time), and provide ratings on craving, mood, and stress using a modified version of the Within Session Rating Scale (Childress et al., 1986). This visual analog scale is anchored with adjectival modifiers ("not at all, mildly, moderately, and extremely"). The scale includes items assessing anxiety, stress, irritability, and craving, and we have utilized it successfully in numerous previous studies. If the session is one of the two daily picture assessments, next a photograph (either stress-related or neutral) will be presented and the participant will be instructed to look at it carefully for 10 seconds. Each picture cue will appear only once during the study. An alarm will sound at the end of each trial, after which participants will complete a post-cue Within Session Rating Scale assessment, ratings of how carefully they looked at the photographs and their distraction level during each trial, and data on their cannabis use since last assessment. If the session is only collecting ambient stress and craving, immediately after the Within Session Rating Scale the participants will be asked to record data on cannabis use since the last assessment session. To encourage CREMA session completion, participants will be compensated \$5.00 for each completed session. Previous studies employing lower incentive strategies have reported 80-90% CREMA completion rates (Gass et al., 2012; Warthen et al., 2009), including in our previous SCOR (Wray et al., 2015); we have slightly increased compensation to maximize potential data collection over the 3-week period. CREMA sessions will begin on Day 2.

f. Progesterone Salivary Sample Collection. Participants will be instructed to collect a saliva sample each morning (1/2 hour after awakening). Samples will be dispensed into containers supplied by study staff and stored in participants' home freezers until bringing the samples to a subsequent study visit for analysis of progesterone levels. These daily home collection and storage procedures have been used in numerous previous studies with excellent participant adherence and sample quality (Edler et al., 2007; Klump et al., 2008). As discussed above in Preliminary Data, we successfully utilized a similar procedure in our last SCOR project. Participants will receive \$10 daily for collection of ovarian hormone salivary samples.

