Data Management and Reduction: All paper-based assessments (other than laboratory reports) will be entered into REDCap, a secure, web-based application designed exclusively to support data capture for research studies. REDCap provides an intuitive interface for data entry (with data validation), audit trails for tracking data manipulation, and automated export procedures for data downloading to statistical packages such as SPSS and SAS. Quarterly database management and data integrity audits will be conducted.

C.2.d. Statistical Considerations

C.2.d.1. **Statistics and Data Analysis** (complete data analytic plan is provided in Biostatistics Resource Core)

Aim 1: Examine the impact of exogenous progesterone on stress cue reactivity and cannabis craving and withdrawal symptoms during a period of cannabis abstinence in the natural environment.

The primary measures of interest are stress and craving ratings in response to stress-related cues using Cue Reactivity Ecological Momentary Assessment (CREMA) in heavy cannabis using women and men. Hypothesis 1: Compared to placebo, progesterone will attenuate reactivity to stress cues presented in the natural environment among women vs. men with CUD. Hypothesis 2: Compared to placebo, progesterone will attenuate cannabis craving and withdrawal symptoms among women vs. men with CUD. To assess these hypotheses multilevel generalized linear mixed effects models with repeated measures (GLMMs) will be developed using CREMA session response data from the 1-week period during active medication administration. Pre-cue stress and craving rating will be centered and used as a time varying covariate in all analysis. Least squares means and associated standard errors will be used for post-hoc comparisons of cue response and CWS scores between treatment group assignments globally as well as time-specific (AM, PM) treatment group differences. Least squares means and associated standard errors will also be used for post-hoc comparisons of craving and stress response between women and men over time. Relevant interactions will be assessed in the models.

Aim 2: Examine the impact of exogenous progesterone on stress cue reactivity during a laboratory stressor task.

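### Aim 1 applies the on-treatment pre-cue rating as a covariate to both hypotheses; this suits cue reactivity (Hypothesis 1) but can shrink a craving-level effect (Hypothesis 2)

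*Combined protocol and SAP*

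**What the plan says.** Section C.2.d.1, Aim 1, sets out two hypotheses. Hypothesis 1 is about reactivity to stress cues. The second reads: "Hypothesis 2: Compared to placebo, progesterone will attenuate cannabis craving and withdrawal symptoms among women vs. men with CUD". One modelling paragraph covers both. The mixed models "will be developed using CREMA session response data from the 1-week period during active medication administration", and the covariate rule follows without distinguishing the hypotheses: "Pre-cue stress and craving rating will be centered and used as a time varying covariate in all analysis". The type of centring is not given. Least squares means are then used for "post-hoc comparisons of cue response and CWS scores between treatment group assignments", and "Relevant interactions will be assessed in the models". The section heading adds that the "complete data analytic plan is provided in Biostatistics Resource Core"; that plan is not among the documents.

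The timing is in C.2.c.3. Under the medication heading: "Dosing will begin in the evening on study day 1". Under CREMA Assessment: "CREMA sessions will begin on Day 2". Each picture session has a rating before and after the cue. The daily session without a picture has a single ambient rating. The CWS, which covers craving as well as withdrawal, is collected in a separate twice-daily survey.

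**The concern.** A covariate measured after randomisation is safe only if treatment does not affect it, or if the target is the effect over and above it. The second condition fits Hypothesis 1: reactivity is the response given the state just before the cue. The team's previous CREMA analysis in smokers (C.1.e) also accounted for pre-cue stress and craving, although it compared the sexes and no randomised drug acting on the pre-cue rating is described.

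Neither condition fits Hypothesis 2 if it is tested on post-cue craving. The covariate is then craving itself, on treatment, and Hypothesis 2 predicts that progesterone lowers it. The pilot in C.1.c points the same way, though weakly (n=8, treatment by time p=0.071). Holding pre-cue craving fixed removes part of the effect being estimated, so a real reduction in craving could be reported as small or absent.

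The rule also cannot be carried out as worded. Neither the CWS nor the ambient ratings have a paired pre-cue rating.

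**Working it through.** **Timing.** First dose: evening of Day 1. First CREMA session: Day 2. No scheduled CREMA rating precedes the first dose, so no pre-cue rating is a baseline.

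**Formula.** Let τ be the treatment-by-sex effect on post-cue craving, δ the same contrast on pre-cue craving, and b the fitted slope of post-cue on pre-cue craving. If the covariate is uncentred or grand-mean centred (the latter moves only the intercept):

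- adjusted estimate ≈ τ − bδ
- fraction kept ≈ 1 − b(δ/τ)

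If it is centred on each person's own mean, and that mean is not put back in the model, the covariate averages zero within every person. It then carries no between-arm difference, and the estimate is τ.

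**Numbers.** The plan gives no b, δ or pre-post correlation, so these are assumed ranges and there is no stated figure to reproduce.

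| b | δ = τ: kept 1 − b | δ = τ/2: kept 1 − 0.5b |
|---|---|---|
| 0.3 | 70% | 85% |
| 0.5 | 50% | 75% |
| 0.7 | 30% | 65% |
| 0.9 | 10% | 55% |

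If δ = 0, 100% is kept.

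**Simulation check.** One treatment contrast, 5,000 per arm, six daily stress-cue ratings, random-intercept model, intraclass correlation 0.3 or 0.6. Progesterone lowers pre-cue craving by 0.5 SD and the shift carries over in full, so the true effect is −0.50. The treatment-by-sex term is the difference of two such contrasts and behaves in the same way.

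- No covariate, or person-mean centring alone: −0.48 to −0.52.
- Grand-mean centring: −0.315 at a fitted slope of 0.36 (formula: −0.50 + 0.36 × 0.50 = −0.32) and −0.026 at 0.96 (formula: −0.50 + 0.96 × 0.50 = −0.02). Kept: 0.315/0.50 = 63% down to 0.026/0.50 = 5%.
- Person-mean centring with the person mean added back: −0.01 to −0.10, or 2% to 20% kept.
- No shift in pre-cue craving, true effect −0.20: every approach gives about −0.2.

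**One centring rule does not serve both hypotheses.** Person-mean centring alone protects a Hypothesis 2 estimate, but under the same carry-over it leaves the whole general shift in the Hypothesis 1 coefficient. The models therefore need to be separated by hypothesis.

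**The case against.** The strongest reply is that the harm needs three conditions, none of which the documents establish: post-cue craving is a Hypothesis 2 outcome, the covariate keeps between-person differences, and progesterone shifts pre-cue craving. The first two would normally be settled in the full plan, which was not supplied. The text also allows a benign reading. Aim 1 names ratings in response to stress cues as its primary measures, then lists cue response and CWS as separate outcomes, with morning and evening contrasts that suit a twice-daily CWS. On that reading Hypothesis 2 rests on the CWS, and pre-cue adjustment serves a legitimate cue-elicited target.

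This stands to the extent that the bias is conditional. It does not clear the rule, because the same paragraph says both hypotheses are assessed with CREMA data, names no other CREMA craving outcome for Hypothesis 2, and applies the covariate throughout.

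A reader might infer three stronger things that the documents do not support:

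- *The Aim 1 craving analysis is biased as planned.* The centring and the Hypothesis 2 outcome are not stated, so this is a risk left open by the wording.
- *Hypothesis 1 is also invalid.* A general shift can leak into a model of stress sessions alone, but Aim 1 specifies no such model. The size also depends on how the shift carries over: if post-cue craving changes only through pre-cue craving, τ = bδ and the adjusted estimate is about zero.
- *The trial loses a definite amount of power.* That would need variances and correlations the plan does not give, and the covariate also reduces noise.

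**Conclusion.** The point holds in conditional form and should be fixed before analysis. The covariate is on treatment, the rule as worded covers Hypothesis 2, and for a craving-level outcome it adjusts for the predicted effect. The size rests wholly on assumed slopes and shifts, and the percentages above are illustrations. The bias arises only when the three conditions under objection hold together; the second is met by an uncentred or grand-mean-centred covariate, or by a person-mean-centred one with the mean added back. Hypothesis 2 is not lost in any case, since the CWS measures craving and withdrawal without a pre-cue rating.

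**What to change.** In C.2.d.1, Aim 1:

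1. Replace the closing words of the covariate sentence, which extend it to every analysis, with: *in the Hypothesis 1 cue-response models only*.
2. Estimate the Hypothesis 2 treatment-by-sex effect on the CWS, and on any CREMA craving outcome the sponsor names, without the on-treatment pre-cue covariate.
3. State the centring used for Hypothesis 1, and whether the person mean enters as well.

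If the Biostatistics Resource Core plan already settles these points, bring C.2.d.1 into line with it. Naming cue type (stress versus neutral) among the Hypothesis 1 interactions would be a useful optional clarification.

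The cost is a text change with no new data collection. The two hypotheses would have slightly different models, and the Hypothesis 2 model gives up any noise reduction the pre-cue rating would have brought.
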